- description of clinic-pathological and oncological characteristics of patients with NSCLC of according to FHC patterns and within-family clusters of other risk factors.

3 Study design

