3.1 General Design

This is a prospective, observational, multi-centre study. Our study population will be represented by consecutive patients with histologically diagnosed NSCLC, regardless of their age, TNM stage, smoking status, and other clinic-pathologic characteristics.

Patients' history will be carefully collected by investigators through a dedicated self-reported study questionnaire, which has been developed for the purpose of this study (provided as **Appendix 1**)

The ad-hoc study questionnaire has been validated by the genetic expert of the steering committee who will train each investigator to translate the returned questionnaire into standardized family trees. Study questionnaire will focus on:

- Family history of cancer;
- Type of tumours/primary tumour site among relatives with history of cancer;
- Age at diagnosis among relatives with history of cancer;
- Biological sex of relatives with history of cancer;

- Exposure to tobacco smoking and smoking habits among relatives with history of cancer;
- Geographical origin of participants and relatives with history of cancer;
- Personal history of multiple malignancies;
- Potential professional and environmental exposure to carcinogens of participants and relatives with history of cancer;
- Ethnicity of both participants and relatives with history of cancer.

To minimize risks of recalling bias, each patient will be given a minimum time of 4 weeks to gather family history information. The study-questionnaire will be then collected at the following clinical consultation as already planned per clinical practice, with no additional study-specific procedures.

During the first study visit all patient's clinic-pathologic will be collected and study participants will be given the ad-hoc questionnaire, which will be returned to the study personnel at the follow-up study visit.

The following clinic-pathologic characteristics will be collected:

- Smoking status (active/passive, package/year, total years of smoking)
- Eastern Cooperative Oncology Group Performance Status (ECOG-PS)
- Age at diagnosis;
- Tumour histology;
- Tumour stage at diagnosis according to the 8th edition of TNM staging system;
- Ethnicity;
- Professional and environmental exposure to carcinogens;
- Programmed death ligand-1 tumour proportion score (PD – L1 TPS)

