- Any available oncogenic drivers including epidermal growth factor receptor (EGFR), Kirsten rat sarcoma virus (KRAS), BRAF, c-MET, mutations and Anaplastic lymphoma kinase (ALK), ROS-1, RET, neurotrophic tyrosine receptor kinase NTRK translocation/gene fusions.

Personal history of other synchronous/metachronous primary malignancies.

Study data will be collected through dedicated electronic case report form (e-CRF). A full list of information that will be collected through the dedicated eCRF (provided as **appendix 2**).

Even though no established FHC criteria exists to refer patients with NSCLC to a genetic counselling for germ-line testing, investigators will assess participant questionnaire at the follow-up study visit and refer patients to genetic counselling when clinically indicated as per local routine practice.

Following collection of participants' questionnaires, we will be able to reconstruct patients' family tree with additional information on how other potential risk factors, such as history of

smoking, exposure to professional/environmental carcinogens, segregate within the relatives with history of cancer.

We will be able to describe whether recurrent family clusters of malignancies/risk factors are specifically associated with risk of lung cancer in order to individuate patients to specifically address to systematic genetic counselling, to assess eligibility for germ-line testing in clinical practice. Secondly, we will also investigate distribution of participants clinic-pathologic characteristics to assess whether any patients and/or tumour-related feature is associated with patterns of FHC and within-family clustering of other risk factors.

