3.4 Study flow-chart

3.5 Study duration

The esteemed study duration is 24 months. Enrolment will start after protocol approval and will last for 12 months. Data analysis will last 12 months from the closure of data collection.

4 Statistical Plan and Sample Size

Given the descriptive nature of the study, and the lack of available data on the relationship between family history of cancer and NSCLC, the minimum sample size for the study has been established on the only study available to date which investigated distribution of FHC among unselected patients with stage IV NSCLC, which described a high familiar burden of cancer (i.e. especially enriched FHC with cases of cancer in both the collateral and lineal family lines) in up to the 6.8% of patients [14]. On the basis of this data, we hypothesized a prevalence of 10% of participants with an especially enriched family history of cancer in our study population; assuming a confidence level of 95% with a total width for the confidence interval of 0.1 (precision of +/- 5%) and considering a 10% drop out, the minimum number of study questionnaire to collect to properly describe the group of interest following a binomial “exact” calculation of the sample size is 175.

Descriptive statistics will be used as appropriate to report FHC data, distribution of within-family other risk factors and baseline clinic-pathologic characteristics. The Fisher exact test and the χ^2 test will be used as appropriate to compare categorical variables (e.g. distribution of baseline characteristics according to the personal/familial positive or negative history). Analyses were performed using the R-studio software, R Core Team (2021). R: A language and environment for statistical computing. R Foundation for Statistical Computing, Vienna, Austria, and the MedCalc® Statistical Software version 20 (MedCalc Software Ltd, Ostend, Belgium; <https://www.medcalc.org>; 2021).

5 Data Management and confidentiality

Data will be collected and retained in accordance with the European General Data Protection Regulation (GDPR) L119, 4 May 2016 and in compliance with other international data protection regulations, such as the title 21 CFR Part 11 of the Code of Federal Regulations, the Health Insurance Portability and Accountability Act of 1996 (HIPAA), and the United Kingdom GDPR.

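### The unadjusted tests in section 4 cannot tell a link with family history from a difference in patient age, which matters for the association aim in section 3.1; the likely size is modest and unknown.

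*Combined protocol and SAP*

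**What the plan says.** The secondary objective in section 2.2 is descriptive: "description of clinic-pathological and oncological characteristics of patients with NSCLC", broken down by FHC pattern and within-family cluster. Section 3.1 (General Design) goes a step further. It plans to "assess whether any patients and/or tumour-related feature is associated with patterns of FHC and within-family clustering of other risk factors".

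Section 4 supplies the methods: descriptive statistics and, for comparisons, "The Fisher exact test and the χ^2 test will be used as appropriate to compare categorical variables". Its example is the "distribution of baseline characteristics according to the personal/familial positive or negative history". No regression model, stratified analysis, matching or other handling of a covariate is named in section 4 or elsewhere.

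Adults enter "regardless of their age, TNM stage, smoking status, and other clinic-pathologic characteristics" (section 3.1). The same section lists "Age at diagnosis" among the patient data to be collected, so the covariate will be in the database.

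**The concern.** A family history is a count that builds up over time. An older patient will tend to have older siblings, cousins and children, who have had longer to develop cancer. If a tumour or patient feature is also more common in younger or in older patients, a two-way table will show it associated with FHC even when there is no link among patients of the same age. The same mechanism can hide a real link.

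The study hopes to find features and patterns that point patients towards genetic counselling. A feature reported as linked to FHC when it only tracks age would mislead that reading, and the planned tests give no means of telling the two apart. The concern does not touch the prevalence description, the sample size, or the comparison of age itself between groups.

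**Working it through.** **1. The plan's own figure.** Section 4 assumes 10% prevalence, 95% confidence, total interval width 0.10 and 10% dropout. The smallest n whose exact (Clopper-Pearson) interval at 10% is no wider than 0.10 is 158 (0.058 to 0.158). Then 158/0.9 = 175.6, against the stated 175. The figure reproduces. It rests on precision for one prevalence, not on any association test, so nothing below changes it. The simulations in steps 3 to 5 use n = 158 (175 × 0.9 = 157.5).

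**2. The mechanism in one line of arithmetic (assumed rates).** Take two equal age groups, younger and older. Let FHC be positive in 40% and 60%, and let a feature be present in 30% and 10%, independently within each group.
- Both present: 0.5×0.4×0.3 + 0.5×0.6×0.1 = 0.09
- FHC positive overall 0.50; feature overall 0.20
- Other cells: 0.50 − 0.09 = 0.41; 0.20 − 0.09 = 0.11; 1 − 0.09 − 0.41 − 0.11 = 0.39
- Crude odds ratio = (0.09 × 0.39)/(0.41 × 0.11) = 0.78, although it is 1 within each age group

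In 4000 simulated studies, chi-square rejects in 9% (N=157) to 10% (N=175). Stronger assumed patterns (FHC 40%/70% or 30%/70%, feature 40%/10%) give 26-29% and 40-44%. An age-stratified Mantel-Haenszel test stays at about 5% in all three. With FHC unrelated or only weakly related to age, the crude test stays at 4-6%.

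**3. Continuous age (assumed model).** Inputs, none from the documents except n:
- mean age 68, SD 10 within feature group; 20% feature, with the feature group younger by the stated gap
- relatives per patient 2 + Poisson(3.5)
- per-relative risk, linear on the logit scale in patient age, from 10% at age 50 to 14% (shallow) or 19% (steep) at age 68
- no feature-FHC link at a given age; outcome any affected relative (55% or 66% of patients)

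Rejection at nominal 5%, shallow to steep slope:

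| Age gap | Chi-square, all relatives' risk rising | Chi-square, parents' risk fixed | Logistic with age (all rising) |
|---|---|---|---|
| 0 years | about 5-6% | – | 4-6% |
| 5 years | about 6-11% | about 5-6% | 4-6% |
| 8 years | about 8-18% | about 5-10% | 4-6% |

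Fisher is lower: at 8 years 7-15% (all rising) and 5-8% (parents fixed). The median crude odds ratio at 8 years is 0.80 or 0.66 with all relatives rising, and about 0.88 or 0.77-0.79 with parents fixed. In the all-rising model the age-adjusted value is 1.00-1.02.

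**4. Enriched group.** Expected size: 158 × 6.8% = 10.7 to 175 × 10% = 17.5, so about 11 to 18 patients. As a stand-in, take three or more affected relatives. With the steep slope (10% of patients) at an 8-year gap, chi-square rejects 8%, Fisher 7%, and Firth with age 4%. With the shallow slope the stand-in covers only 4% of patients and shows no inflation.

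**5. Rare features.** For a 2% feature, 36-42% of runs have an empty cell, so ordinary logistic regression is unsuitable.

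**6. Price of adjusting.** Standard-error inflation = 1/√(1 − r²), with r² = 0.16·gap²/(100 + 0.16·gap²) and 0.16 = 0.2 × 0.8.
- 8 years: r² = 10.24/110.24 = 0.093, inflation 1.05
- 10 years: r² = 16/116 = 0.138, inflation 1.08

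**The case against.** Section 4 opens by calling the study descriptive, section 2.2 asks for description, and the sentence in section 3.1 says associated, not independently associated. A crude association is a legitimate answer to that wording. This stands, and it is why the crude tests should stay and why a clear crude-and-descriptive label is acceptable where no model is fitted.

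The size is assumed throughout. The larger rates need every relative's risk to rise with the patient's age. Many patients' parents will already have lived most or all of their lives, and fixing their risk roughly halves the inflation. If older patients know less about relatives' diagnoses, the age slope could be weaker still. This stands too.

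Age adjustment is also partial and not neutral. It leaves smoking and occupational or environmental exposures untouched, and these are the clustering the protocol itself stresses. Inherited predisposition may lower age at diagnosis, so adjustment can remove signal. In the least favourable assumed case (relatives' risk unrelated to patient age, age lowered by 10-15 years) an enriched-group odds ratio of 1.56 becomes 1.49-1.42. This is a reason to show both estimates, not to omit one.

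A reader might infer that the planned tests are wrong, or that the study will report false links. The documents support neither: the tests fit the descriptive objective, and nothing in the text shows how age relates to any feature or to FHC.

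**Conclusion.** The point holds in a limited form and is one to consider. For the association aim in section 3.1, unadjusted tests cannot separate a link with FHC from an age difference when age is related to both, and the plan names nothing else. The size is unknown. Under the stated assumptions, crude chi-square rejection at an 8-year age gap lies between about 5% and 18%, depending mainly on whether parents' risk varies with patient age. It is near nominal when the gap is small or FHC is only weakly related to age.

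Two stronger inferences should be resisted. One is that the enriched group, for which section 4 says "we hypothesized a prevalence of 10% of participants with an especially enriched family history of cancer in our study population", is seriously affected. The inflation there is at most small, and three or more affected relatives is only a stand-in for the protocol's description, which refers to both collateral and lineal lines. The other is that an age-adjusted odds ratio would establish an independent link. It would deal with age alone.

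**What to change.** In section 4:
- Keep Fisher and chi-square as the crude description.
- For each feature other than age at diagnosis compared by positive or negative family history, add an exploratory logistic regression. FHC positive/negative is the outcome; the covariates are the feature (as a factor if it has several levels, such as stage or histology) and continuous age at diagnosis. Report crude and age-adjusted odds ratios with 95% confidence intervals side by side.
- For rare features, such as uncommon oncogenic drivers, and for the enriched group, use a Firth model with age as the only covariate besides the feature, or description only.
- State that the adjusted estimate addresses age and not smoking or exposures, and that predisposition may itself lower age at diagnosis, so neither estimate replaces the other.
- Where no adjusted estimate is given, state that the comparison is crude and descriptive and does not establish a link independent of age.

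The cost is a few sentences, a little analysis work, and a standard error about 5-8% wider at age gaps of 8-10 years. No new data are needed, and the target of 175 questionnaires stays as it is.
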